8.2.2. Response Criteria

For patients in Cohort C, response will be determined based on disease presentation. Investigators will assess response based on the following response criteria:

- Treatment Response Criteria for MDS/MPN ([Savona et al. 2015](#))
- Response Evaluation Criteria in Lymphoma (RECIL 2017) ([Younes et al. 2017](#))
- International Working Group (IWG) Response Criteria for AML ([Cheson et al. 2003](#))

A review of the response assessments will be conducted by an adjudication committee.

8.2.3. Response Definitions

Response will be determined based on Investigators' assessment of imaging, bone marrow, peripheral blood, and extramedullary disease. Assessments will be based on the definitions described in [Table 14](#).

Table 14: Response Definitions for Cohort C

MLN Characteristic	MLN Only	Lymphoma Presentation	Leukemia Presentation
Response Criteria	Savona 2015 ^a	RECIL 2017 ^b	Cheson 2003 ^c
Complete response (CR)	Must fulfill all criteria defined for CR	Must fulfill all criteria defined for CR	
 Must fulfill all criteria defined for morphologic complete response CR does not include: 
 Morphologic leukemia-free state Complete response with incomplete hematological recovery (CRi), or Cytologic complete response (CRc)
Partial response (PR)	Must fulfill all criteria defined for PR	Must fulfill all criteria defined for PR	Must fulfill all criteria defined for partial remission
Complete response with incomplete blood count recovery (CRi)	N/A	N/A	Must fulfill all criteria defined for CRi
Complete cytogenetic response (CCyR)	Resolution of previously present chromosomal abnormality known to be associated with MLN (eg. 8p11 translocation)	Must fulfill all criteria defined for CCyR (Savona 2015) ^a	Must fulfill all criteria defined for cytogenetic complete response (CRc) (Cheson 2003) ^c and CCyR (Savona 2015) ^a
Partial cytogenetic response (PCyR)	≥50% reduction of chromosomal abnormality known to be associated with MLN (eg. 8p11 translocation)	Must fulfill all criteria defined for PCyR (Savona 2015) ^a	Must fulfill all criteria defined for PCyR (Savona 2015) ^a
PD/Relapsed disease	Must fulfill all criteria defined for PD/relapsed disease	Must fulfill all criteria defined for PD/relapsed disease	Must fulfill all criteria defined for PD/relapsed disease

^a Savona, et al. An international consortium proposal of uniform response criteria for myelodysplastic/myeloproliferative neoplasms (MDS/MPN) in adults. *Blood*. 2015.

^b Younes, et al. International Working Group consensus response evaluation criteria in lymphoma (RECIL 2017). *Ann Oncol*. 2017.

^c Cheson, et al. Revised recommendations of the International Working Group for Diagnosis, Standardization of Response Criteria, Treatment Outcomes, and Reporting Standards for Therapeutic Trials in Acute Myeloid Leukemia. *J Clin Oncol*. 2003.

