Table 4:	Objectives and Endpoints (Cohorts A and B).....	38
Table 5:	Objectives and Endpoints: Cohort C	39
Table 6:	Dose Modifications for Related Nonhematologic Toxicities	50
Table 7:	Dose Modifications for Related Ocular Toxicities.....	51
Table 8:	Recommendations for Hyperphosphatemia Management.....	52
Table 9:	Futibatinib Dose Interruption and Modification Criteria for Related Hematologic Toxicities for Patients in Cohorts A and B	53
Table 10:	Pharmacokinetic Blood Sample Collection	62
Table 11:	Target and Non-target Lesions	66
Table 12:	Time Point Response for Patients with Target (\pm Non-target) Disease.....	67
Table 13:	Time Point Response for Patients with Only Non-target Disease	68
Table 14:	Response Definitions for Cohort C.....	69
Table 15:	Observed ORR with Exact 95% Confidence Interval (Cohort A).....	77
Table 16:	Observed ORR with Exact 95% Confidence Interval (Cohort B).....	78
Table 17:	Observed CR Rate with Exact 95% Confidence Interval (Cohort C)	78
Table 18:	Definitions of Analysis Populations	79

LIST OF FIGURES

Figure 1:	Study Schema	40
-----------	--------------------	----

LIST OF ABBREVIATIONS AND DEFINITIONS OF TERMS

Abbreviation	Definition
AE	Adverse event
AML	Acute myeloid leukemia
ANC	Absolute neutrophil count
ALT	Alanine aminotransferase
ASCO	American Society of Clinical Oncology
AST	Aspartate aminotransferase
BCR	Breakpoint cluster region (gene)
BCRP	Breast cancer resistance protein
CCA	Cholangiocarcinoma
CI	Confidence interval
CR	Complete response
CCyR	Complete cytogenetic response
COVID-19	Coronavirus Disease of 2019
CrCl	Creatinine clearance
CRc	Cytologic complete response per IWG response criteria for AML (Cheson et al. 2003)
CRi	Complete response with incomplete hematological recovery
CT	Computed tomography
CTCAE	Common Terminology Criteria for Adverse Events
ctDNA	Circulating tumor DNA
CYP	Cytochrome P450

Abbreviation	Definition
DCR	Disease control rate
DOOR	Duration of response
ECG	Electrocardiogram
ECOG	Eastern Cooperative Oncology Group
eCRF	Electronic case report form
EFS	Event-free survival
EMA	European Medicines Agency
EOT	End of treatment/end of therapy
FDA	Food and Drug Administration
FGFR	Fibroblast growth factor receptor
FISH	Fluorescence in situ hybridization
GEJ	Gastro-esophageal junction
GCP	Good Clinical Practice
HSCT	Hematological stem cell transplant
IB	Investigator's Brochure
iCCA	Intrahepatic cholangiocarcinoma
ICF	Informed consent form

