
 To assess the possible impact of genetic alterations or other laboratory abnormalities on the efficacy of futibatinib To assess the population pharmacokinetics (popPK) and exposure response 	
 Assessment of genetic alterations in circulating tumor DNA (ctDNA), tumor biopsy, and/or plasma samples, and their possible correlation with clinical outcome. PK data will be pooled with data from other cohorts or other studies for a popPK analysis. The relationship between popPK model derived exposure and response will be explored

Table 5: Objectives and Endpoints: Cohort C

Overall Objective	
The overall objective of Cohort C is to assess the clinical activity of futibatinib as monotherapy in the treatment of patients with MLN harboring FGFR1 rearrangements.	
Primary	
To evaluate complete response (CR) rate	CR rate, defined as the proportion of patients who achieved a CR.
Secondary	

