2.2.2.2. Secondary Endpoints

The definition of the secondary endpoints is shown below:

- ORR is defined as the proportion of patients who achieved a CR, CRi, or PR;
- CR+CRi rate is defined as the proportion of patients who achieved a CR or CRi;
- CCyR rate is defined as the proportion of patients who achieved CCyR;
- PCyR rate is defined as the proportion of patients who achieved PCyR;
- Duration of CR is defined as the time from the first documentation of CR to the first documentation of objective tumor progression or death due to any cause, whichever occurs first;
- Duration of CR+CRi is defined as the time from the first documentation of CR or CRi to the first documentation of objective tumor progression or death due to any cause, whichever occurs first;
- DOR is defined as the time from the first documentation of CR, CRi, or PR to the first documentation of objective tumor progression or death due to any cause, whichever occurs first;
- PFS is defined as the time from first dose of study therapy to the date of death (any cause) or disease progression, whichever occurs first;
- RFS is defined as the time from the first documentation of CR to the first documentation of disease relapse or death due to any cause, whichever occurs first;
- Only for leukemia presentation, EFS is defined as the time from first dose of study therapy to treatment failure, disease relapse after CR, or patient death from any cause. Treatment failure for EFS is defined as PD in this study;
- OS is defined as the time from the date of first dose to the death date; and
- Safety is based on reported AEs and on-study laboratory parameters, graded according to the NCI CTCAE V5.0.

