5.5.2.1. Primary Efficacy Analysis

CR rate will be calculated and the 2-sided 95% CI will be derived by Clopper–Pearson method.

The confirmation of the best objective response of CR with at least 4 weeks interval of two consecutive time points is not required; however, CR must be confirmed by a minimum of 2 bone marrow assessments when the first response assessment shows marrow fibrosis. If applicable, responses recorded after disease progression or initiation of new anticancer treatment will be excluded.

Response will be determined based on disease presentation, and Investigators will assess response based on the Response Definition described in [Table 14](#). All the response assessments by Investigators will be adjudicated by a response adjudication committee.

Table 14: Response Definitions for Cohort C

MLN Characteristic	MLN Only	Lymphoma Presentation	Leukemia Presentation
Response Criteria	Savona 2015 ^a	Younes 2017 ^b	Cheson 2003 ^c
Complete response (CR)	Must fulfill all criteria defined for CR	Must fulfill all criteria defined for CR	Must fulfill all criteria defined for morphologic complete response CR does not include: 
 • morphologic leukemia-free state • complete response with incomplete hematological recovery (CRi), or cytologic complete response (CRc)
Partial response (PR)	Must fulfill all criteria defined for PR	Must fulfill all criteria defined for PR	Must fulfill all criteria defined for partial remission
Complete response with incomplete blood count recovery (CRi)	N/A	N/A	Must fulfill all criteria defined for CRi
Complete cytogenetic response (CCyR)	Resolution of previously present chromosomal abnormality known to be associated with MLN (eg. 8p11 translocation)	Must fulfill all criteria defined for CCyR	Must fulfill all criteria defined for cytogenetic complete response (CRc) and CCyR

^a Savona, et al. An international consortium proposal of uniform response criteria for myelodysplastic/myeloproliferative neoplasms (MDS/MPN) in adults. *Blood*. 2015.

^b Younes, et al. International Working Group consensus response evaluation criteria in lymphoma (RECIL 2017). *Ann Oncol*. 2017.

^c Cheson, et al. Revised recommendations of the International Working Group for Diagnosis, Standardization of Response Criteria, Treatment Outcomes, and Reporting Standards for Therapeutic Trials in Acute Myeloid Leukemia. *J Clin Oncol*. 2003.

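### Cohort C, leukemia presentation: Table 14 bars CRc from CR but requires CRc for complete cytogenetic response, so the text does not settle whether a complete cytogenetic responder counts in the primary CR rate

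*Protocol*

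**What the plan says.** The primary endpoint of Cohort C is the "CR rate, defined as the proportion of patients who achieved a CR" (Protocol Section 2, Table 5). What counts as a CR depends on disease presentation and is set out in Protocol Table 14 (Section 8.2.3) and SAP Table 14 (Section 5.5.2.1).

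For the leukemia presentation, the CR cell has two parts. The first is a positive criterion: "Must fulfill all criteria defined for morphologic complete response". The second is a list opened by "CR does not include". It names morphologic leukemia-free state, CRi and, as its third item, "Cytologic complete response (CRc".

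In the same column the CCyR row reads "Must fulfill all criteria defined for cytogenetic complete response (CRc", and adds the CCyR criteria from the MDS/MPN source. SAP Table 14 carries the same exclusion, "cytologic complete response (CRc", and the same CCyR requirement. The protocol's abbreviation list has one entry for CRc: "Cytologic complete response per IWG response criteria for AML".

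For the secondary endpoints, SAP Section 2.2.2.2 states that "ORR is defined as the proportion of patients who achieved a CR, CRi, or PR". The CR+CRi rate counts CR or CRi. Neither endpoint names CRc. The MLN-only and lymphoma columns contain no such exclusion.

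**The concern.** One abbreviation, tied to one cited set of AML criteria, has two expansions. Under one it is kept out of CR; under the other it is a condition for CCyR. If the two entries are the same category, then CCyR implies CRc, CRc is not CR, and a complete cytogenetic responder in the leukemia presentation cannot count toward the primary CR rate. Unless that patient is classed as CRi or PR, the same patient is also outside CR+CRi and ORR, and is then a complete cytogenetic responder and a non-responder at once.

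Other endpoints inherit the question. Duration of CR and RFS are restricted to patients with CR. The EFS rules in SAP Table 17 differ by whether a CR was achieved: for a patient still on treatment without an event, the censoring date is the last response assessment if there was a CR and the last contact if there was not.

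An adjudication committee reviews the responses, but neither document gives it a rule for a patient who meets both morphologic CR and CRc. In an open-label, single-arm cohort of 20, a choice made after responses are known could decide the primary result.

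**Working it through.** **The plan's own figures.** Protocol Section 11.1 gives n = 20, a null CR rate of 10%, a target of 50%, a 2-sided alpha of 5%, success at 6 or more responders, and power over 95%. With P(X ≥ r | n, p) = Σ C(n,k) pᵏ(1−p)ⁿ⁻ᵏ, summed from k = r to n:

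- Power: P(X ≥ 6 | 20, 0.50) = 97.9%, which agrees with the stated figure.
- Type I error: P(X ≥ 6 | 20, 0.10) = 1.13%, below 2.5%. At 5 responders the tail is 4.3%, so 6 is the correct threshold.
- Clopper–Pearson 95% CI for 6/20: 11.9% to 54.3%, as stated.

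No design figure is in dispute.

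**One patient at the threshold.** Removing one responder from 6/20 leaves 5/20. The exact 95% CI is then 8.7% to 49.1%, and the lower bound no longer excludes 10%. Each patient moves the observed rate by 1/20 = 5 percentage points.

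**The two readings of the CR cell.**

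| Patient in leukemia presentation | Literal exclusion | List names categories that do not qualify on their own |
|---|---|---|
| Meets all morphologic CR criteria, not CRc | CR | CR |
| Meets all morphologic CR criteria and CRc | Not CR | CR |
| Meets CRc but not all morphologic CR criteria (if possible under the cited source) | Not CR | Not CR |

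The readings differ only in the second row, and the documents contain no sentence about that patient.

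**Sensitivity under the literal reading.** Let L be the share of expected CRs that occur in leukemia-presentation patients and c the share of those removed because they are also CRc. The documents give neither, so both are assumptions. If the CR rate is the same in every presentation, L is also the leukemia share of the cohort. The countable rate is p = 0.50 × (1 − L × c), and power is P(X ≥ 6 | 20, p).

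| L | c | p | Power |
|---|---|---|---|
| any | 0 | 0.500 | 97.9% |
| 0.25 | 0.50 | 0.4375 | 93.1% |
| 0.25 | 1.00 | 0.375 | 82.1% |
| 0.50 | 0.50 | 0.375 | 82.1% |
| 0.50 | 1.00 | 0.250 | 38.3% |

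The first row is also the result under the milder reading.

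**The case against.** The strongest reply is that the operative line of the CR cell is the positive one: a patient who fulfils every morphologic CR criterion is a CR. The list that follows then only names categories that do not qualify by themselves, and also meeting CRc takes nothing away. This reading is possible. Against it, the list then adds no restriction, since the first line already demands all the criteria, and a programmer or adjudicator could reasonably give it effect. CRi, in the same list, is handled as a separate category with its own row and endpoint, whereas CRc has no row of its own and no place in ORR.

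Second, the two CRc entries may not be the same category. The excluded one is spelled cytologic in both tables and in the abbreviation list. If a distinct category was meant, no cytogenetic responder is excluded and the fault is a duplicated abbreviation. The shared source makes identity likely, but the documents do not prove it.

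Third, the endpoint counts patients who achieved a CR. One documented in morphologic CR before cytogenetic clearance may already count, and no text revokes that CR. Even a literal exclusion could therefore reach fewer patients than the sensitivity table assumes.

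A reader might also infer that the rule penalises the deepest remissions. That depends on how the cited AML criteria define and rank CRc, and neither document reproduces them. Nor can one say that the secondary endpoints are all biased downward. CR+CRi and ORR can only lose responders, but duration of CR and RFS would lose patients from the analysis, with unknown direction.

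**Conclusion.** The contradiction stands, and it lies in the definition of Cohort C's sole primary endpoint. The leukemia column excludes a category labelled CRc from CR and requires a category labelled CRc for CCyR, in both protocol and SAP, and no other passage resolves it. The ambiguity is confined to one of the three presentations.

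The documents do not establish that complete cytogenetic responders will be counted as non-responders; that is the literal reading, and the text does not decide between it and the milder one. Nor do they establish a loss of power. The effect is none under the milder reading, or if cytologic was meant as a separate category. Under the literal reading with the assumed shares above, power is 93%, 82% or 38% instead of 97.9%. The lowest figure needs half of the expected CRs to come from leukemia-presentation patients and every one of those to be removed.

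What needs no assumed shares is the fragility at the threshold: one patient reclassified from 6/20 to 5/20 reverses the conclusion against 10%. The point should be settled before any Cohort C analysis.

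**What to change.** Before any Cohort C analysis, make these changes in Protocol Table 14, SAP Table 14 and the abbreviation list:

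1. Check CRc against the cited AML criteria and use one expansion per abbreviation throughout.
2. State in the leukemia CR cell of both tables that a patient who meets all morphologic CR criteria counts as a CR whether or not cytogenetic complete response is also met.
3. If a separate cytologic category was intended, give it its own abbreviation and definition.

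The adjudication committee should work from the same sentence. The cost is a line in each table and one abbreviation entry. No new data, visits or analyses are needed, and the planned threshold and power stay as stated.

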8.3. Efficacy Endpoints

The efficacy endpoints are provided in [Table 4](#). Definitions of each endpoint are provided in Section [11.5.3.1.2](#) . For further information, refer to the SAP.

9. SAFETY EVALUATIONS

9.1. Adverse Events

An AE is defined as any untoward medical occurrence in a clinical study patient and does not necessarily have a causal relationship with the study drug. An AE can therefore be any unfavorable and unintended sign (including an abnormal finding), symptom, or disease temporally associated with the use of a study drug, whether or not related to the study drug. This includes any occurrence that is new in onset or aggravated in severity or frequency from the baseline condition, or abnormal results of diagnostic procedures, including laboratory test abnormalities. For this study, progression of the cancer under study is not considered an AE unless the Investigator deems it related to study drug.

All AEs will be collected from the time informed consent has been documented through 30 days after the last dose of any study drug (safety follow-up) or until the start of new antitumor therapy, whichever is earlier. Any untoward medical event that occurs after the safety follow-up is not considered an AE, unless the Investigator considers that the AE is related to the study drug.

Signs and symptoms of a preexisting disease should not be considered an AE, but should rather be considered baseline signs and symptoms. Clinically significant worsening of preexisting signs and symptoms is considered an AE.

9.2. Reporting of Adverse Events

9.2.1. Terms of Reported Adverse Events

All AEs will be documented in the eCRF according to the eCRF Completion Guidelines. Documentation should include onset and resolution/stabilization dates, severity/grade, relationship to study drug, and outcome of the event.

When a diagnosis for the reported signs or symptoms is known, the Investigator should report the diagnosis, not the symptoms, as the AE.

Adverse events can be spontaneously reported or elicited during open-ended questioning, examination, or evaluation of a patient. In order to prevent reporting bias, patients should not be questioned regarding the specific occurrence of one or more AEs.

9.2.2. Severity of Adverse Events

The NCI-CTCAE V5.0 will be used to grade the severity of AEs.

9.2.3. Causal Relationship with Study Drug

The causal relationship between an AE and study drug will be assessed using the following 2-point scale, taking into account the patient's condition, medical history, concomitant medications, and the temporal relationship between study drug administration and onset of the event.

1. An AE is considered to be “Related” if the event follows a reasonable temporal sequence from administration of study drug and there is a reasonable possibility that at least one of the following conditions is true:
 - A positive dechallenge: This means that the event improves or resolves after the drug is stopped (temporarily or permanently).
 - A positive rechallenge: This means that the event reappears after the drug is restarted.
 - The event cannot be reasonably explained by the patient’s clinical state and/or other therapies administered.
 - A single occurrence of an event that is uncommon and known to be strongly associated with drug exposure (eg, angioedema, Stevens-Johnson syndrome).
2. An AE is considered to be “Not related” if there is no reasonable possibility that at least one of the following conditions is true:
 - The event occurred prior to study drug administration.
 - There is no reasonable possibility that the study drug caused the event. (“No reasonable possibility” means there is no evidence to suggest a causal relationship between the study drug and the AE)
 - The event does not follow a reasonable temporal sequence from administration of study drug and could have been produced by a documented preexisting condition, concomitant medication, or patient’s clinical state.

9.2.4. Outcome of Adverse Events

Record the outcome of AEs as follows:

- Resolved
- Not resolved
- Fatal

9.2.5. Follow-up of Adverse Events

Any ongoing AEs should be followed until the earliest occurrence of one of the following:

- The AE has resolved or stabilized
- Completion of Safety Follow-Up Visit
- Start of new antitumor therapy
- Withdrawal of consent
- Death
- Other (eg, transfer to another hospital)

9.3. Laboratory Assessments

9.3.1. Reporting and Evaluation of Laboratory Test Results

All laboratory results must be reviewed by the Investigator. A new laboratory abnormality that has a clinical impact on a patient (including eg, resulting in study drug dose reduction, treatment delay, treatment discontinuation, or requirement of intervention) is considered an AE, unless it is considered part of clinical manifestations to a clinical diagnosis that is already reported as an AE.

All laboratory values that are out of the normal range are to be evaluated for their clinical impact before exposing the patient to the next dose of futibatinib.

The NCI-CTCAE V5.0 will be used to grade the severity of laboratory data.

9.3.2. Repeat Testing

Evaluation of any clinically significant laboratory test will be repeated, as clinically indicated, until the value returns to the baseline level or clinically stabilizes, or until another treatment is given.

9.4. Serious Adverse Events

9.4.1. Definitions of Serious Adverse Events

An SAE is any untoward medical occurrence that at any dose:

- Results in death
 - Death due to disease progression or relapse is not considered an SAE unless the Investigator deems it related to the study drug.
- Is life-threatening
 - The term "life-threatening" refers to an event in which the patient was at risk of death at the time of the event; it does not refer to an event which hypothetically might have caused death if it were more severe.
- Requires inpatient hospitalization or prolongation of existing hospitalization. The following are not considered hospitalizations for the purposes of assessing seriousness (however, one of the other serious criteria may apply):
 - Emergency room visits <24 hours
 - Hospitalizations for pre-planned procedures
 - Hospitalization for study-related treatment and procedures
- Results in persistent or significant disability/incapacity, where disability is defined as a substantial disruption of a person's ability to conduct normal life functions, either reported or defined as per clinical judgment.
- Is a congenital anomaly/birth defect (if exposure to product just before conception or during pregnancy resulted in an adverse outcome in the child).

- Is any other important medical event that based upon appropriate medical judgement may jeopardize the patient or may require medical or surgical intervention to prevent one of the other outcomes listed in the definitions above (eg, may not result in death, be life-threatening, or require hospitalization).

